3.4.2 Doses and treatment regimens

On the morning of Day 1 of each Treatment Period (A, B, C) all volunteers will receive a single dose of rosuvastatin calcium, atorvastatin calcium or simvastatin according to their assigned Treatment Sequence under fasting conditions. (See Restrictions Section 3.3.4). Tablets will be taken orally with 240 mLs of distilled, room temperature water. Tablets are not to be crushed or chewed. Volunteers must remain in an upright position (sitting or standing) for 4 hours after dosing.

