4.4 Safety measurements

4.4.1 Laboratory safety measurements

Blood and urine samples for determination of drugs of abuse, clinical chemistry, hematology, urinalysis, and pregnancy will be taken at the times give in the study plan ([Table 1](#)). The date and time of collection will be recorded on the appropriate CRF.

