4.7.1 Adverse Events

4.7.1.1 Definitions

The definitions of adverse events (AEs), serious adverse events (SAEs) and other significant adverse events (OAEs) are given below. It is of the utmost importance that all staff involved in the study is familiar with the content of this section. The principal investigator is responsible for ensuring this.

Adverse event

An adverse event is the development of an undesirable medical condition or the deterioration of a pre-existing medical condition following or during exposure to a pharmaceutical product, whether or not considered causally related to the product. An undesirable medical condition can be symptoms (e.g., nausea, chest pain), signs (e.g., tachycardia, enlarged liver) or the abnormal results of an investigation (e.g., laboratory findings, electrocardiogram). In clinical studies, an AE can include an undesirable medical condition occurring at any time, including run-in or washout periods, even if no study treatment has been administered.

Serious adverse event

A serious adverse event is an AE occurring during any study phase (i.e., run-in, treatment, washout, follow-up), and at any dose of the investigational product, comparator or placebo, that fulfills one or more of the following criteria:

- Results in death
- Is immediately life-threatening
- Requires in-patient hospitalization or prolongation of existing hospitalization
- Results in persistent or significant disability or incapacity
- Is a congenital abnormality or birth defect
- Is an important medical event that may jeopardize the volunteer or may require medical intervention to prevent one of the outcomes listed above.

The causality of SAEs (i.e., their relationship to study treatment) will be assessed by the investigator(s), who in completing the relevant case report form must answer “yes” or “no” to the question “Do you consider that there is a reasonable possibility that the event may have been caused by any of the following – study medication – other medication?” For further guidance on the definition of a SAE and a guide to the interpretation of the causality question, see [Appendix B](#) to the Clinical Pharmacology Study Protocol.

Note that SAEs that could be associated with any study procedure should also be reported. For such events the causal relationship is implied as “yes”.

Other Significant Adverse Events (OAE)

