4.7.1.2 Recording of adverse events

Adverse events will be collected beginning Day –1A through the final assessment of the final treatment period. SAEs will be collected from the time the informed consent is signed through final assessment of the final treatment period.

The following will be recorded for each AE:

- Start date
- Stop date
- Maximum intensity

- Action taken
- Outcome
- Causality (yes or no)
- Whether conditions constitute and SAE

The intensity rating is defined as:

- mild (awareness of sign or symptom, but easily tolerated)
- moderate (discomfort sufficient to cause interference with normal activities)
- severe (incapacitating, with inability to perform normal activities)

It is important to distinguish between serious and severe AEs. Severity is a measure of intensity whereas seriousness is defined by the criteria in Section 4.7.1.1. An AE of severe intensity need not necessarily be considered serious. For example, nausea that persists for several hours may be considered severe nausea, but not a SAE. On the other hand, a stroke that results in only a limited degree of disability may be considered a mild stroke but would be a SAE.

Should a pregnancy occur, it must be reported in accordance with the procedures described in Section 8.3. Pregnancy in itself is not regarded as an AE unless there is a suspicion that an investigational product may have interfered with the effectiveness of a contraceptive medication.

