6.2.1.1 Adverse events

Adverse events will be summarized by System Organ Class and Preferred Term, using medical dictionary for regulatory activities (MedDRA). All adverse event data will be listed for all volunteers. Separate listings of all serious adverse events, deaths or other significant adverse events will be presented.

Safety data will be summarized and listed by study medications and ethnic groups.

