Appendix Date

Additional Safety Information

FURTHER GUIDANCE ON THE DEFINITION OF A SERIOUS ADVERSE EVENT (SAE)

Life threatening

‘Life-threatening’ means that the subject was at immediate risk of death from the AE as it occurred or it is suspected that use or continued use of the product would result in the subject’s death. ‘Life-threatening’ does not mean that had an AE occurred in a more severe form it might have caused death (eg, hepatitis that resolved without hepatic failure).

Hospitalisation

Out-patient treatment in an emergency room is not in itself a serious AE, although the reasons for it may be (eg, bronchospasm, laryngeal oedema). Hospital admissions and/or surgical operations planned before or during a study are not considered AEs if the illness or disease existed before the subject was enrolled in the study, provided that it did not deteriorate in an unexpected way during the study.

Important medical event or medical intervention

Medical and scientific judgement should be exercised in deciding whether a case is serious in situations where important medical events may not be immediately life-threatening or result in death, hospitalisation, disability or incapacity but may jeopardize the subject or may require medical intervention to prevent one or more outcomes listed in the definition of serious. These should usually be considered as serious.

Simply stopping the suspect drug does not mean that it is an important medical event; medical judgement must be used.

Examples of such events are:

- Angioedema not severe enough to require intubation but requiring iv hydrocortisone treatment
- Hepatotoxicity caused by paracetamol (acetaminophen) overdose requiring treatment with N-acetylcysteine
- Intensive treatment in an emergency room or at home for allergic bronchospasm
- Blood dyscrasias (eg, neutropenia or anaemia requiring blood transfusion, etc) or convulsions that do not result in hospitalisation
- Development of drug dependency or drug abuse.

A GUIDE TO INTERPRETING THE CAUSALITY QUESTION

The following factors should be considered when deciding if there is a “reasonable possibility” that an AE may have been caused by the drug.

- Time Course. Exposure to suspect drug. Has the subject actually received the suspect drug? Did the AE occur in a reasonable temporal relationship to the administration of the suspect drug?

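### Adverse event onset is listed by date only, so Day 1 events before the dose cannot be separated from those after it in the by-statin safety summary

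*Protocol*

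**What the plan says.** Protocol section 4.7.1.2 introduces the adverse event fields with "The following will be recorded for each AE". The list is start date, stop date, maximum intensity, action taken, outcome, causality as a yes/no answer, and whether the event is serious. No time of day appears, and the causality item as listed does not name a statin.

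The same section sets the collection window: "Adverse events will be collected beginning Day –1A through the final assessment of the final treatment period". The definition in section 4.7.1.1 counts events at any time, "including run-in or washout periods, even if no study treatment has been administered".

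On dosing, section 3.4.2 states: "On the morning of Day 1 of each Treatment Period (A, B, C) all volunteers will receive a single dose". The clock hour is not given. On reporting, section 6.2.1.1 states: "Safety data will be summarized and listed by study medications and ethnic groups".

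Elsewhere clock time is required. For laboratory safety samples, section 4.4.1 says: "The date and time of collection will be recorded on the appropriate CRF". The causality guide in Appendix B asks: "Did the AE occur in a reasonable temporal relationship to the administration of the suspect drug".

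**The concern.** Every dose falls inside a calendar date, and the by-statin summary needs to know on which side of the dose an event began. A date does not show this on Day 1. A headache dated Day 1A may have started before any drug was given. One dated Day 1B or 1C may have started while the only statin so far taken was the previous period's.

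This matters more in a single-dose study than in a long one, because hours count. The protocol gives peak times of 3 to 5 hours for rosuvastatin (section 1.1.1), and its appended product brochures give 1 to 2 hours for atorvastatin and 1.3 to 2.4 hours for simvastatin's inhibitors. Complaints before dosing are also plausible: Day 1 opens with a 10-hour fast and a pre-dose blood draw, and Period A adds a fasting lipid sample before dosing.

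At stake is the accuracy of the adverse event counts by statin, which serve the secondary objective on safety and tolerability. An analysis plan can choose a rule for placing Day 1 events, but it cannot recover an onset time that was not collected.

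**Working it through.** There is no stated figure to reproduce. The check is a reading of the text plus a calculation to size the affected window.

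**Can the listed fields order onset against dose?**

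| Onset | Date alone sufficient? | Possible error |
|---|---|---|
| Day -1A | Yes, before any dose | None |
| Day 1A | No | No drug against first statin |
| Days 2 to 4 of a period | Yes, after that period's dose | None |
| Washout, Day -1B, Day -1C | Yes, after the previous dose and before the next | None |
| Days 1B and 1C | No | Previous against current statin |

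The ambiguity is confined to three dates per volunteer. Only two of them can confuse one statin with another.

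**How large is the window?**

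Inputs from the protocol: three in-patient periods of 5 days and two washouts of at least 7 days (synopsis, section 3.1).

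- Calendar days: 3 × 5 + 2 × 7 = 29, which agrees with the 29-day study in the synopsis.
- Hours: 29 × 24 = 696.
- Day 1 dates: 3 / 29 = 10.3% of dates.

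Input assumed: dosing between 07:00 and 10:00, so h = 7 to 10 pre-dose hours after midnight. The protocol says only morning.

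- Share of one Day 1 before dosing: h / 24 = 7/24 to 10/24 = 29% to 42% of clock hours.
- Share of study time, three dosing days: 3h / 696 = 21/696 to 30/696 = 3.0% to 4.3%.
- Share where two statins could be confused (Periods B and C): 2h / 696 = 14/696 to 20/696 = 2.0% to 2.9%.

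These use whole calendar days and the minimum washout. A longer washout lowers the shares of study time. They are shares of time, and they become shares of events only if onset is uniform over the clock, which the documents give no reason to assume.

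**The case against.** The strongest reply has four parts.

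First, a reader might infer that pre-dose events will be credited to the wrong statin. The protocol does not support that. It contains no rule for assigning an event to a study medication; section 6.2.1.1 fixes only the grouping of the summary. Such a rule is ordinary analysis-plan content, so its absence here is no fault, and the direction of any error is not fixed. On Day 1A there is no earlier statin to which an event could belong. This part stands in full.

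Second, a reader might infer that the time-course question in Appendix B cannot be answered. It can. Causality is the investigator's judgement, volunteers are in-patients on Day 1, and site personnel supervise dosing (section 3.4.5). The person answering can know whether onset preceded the tablet. This also stands. What the listed fields lack is a record of that order for anyone working later from the data.

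Third, a reader might take about a third of Day 1 events as misassigned. That needs uniform onset over 24 hours, sleep included, and a rule sending every Day 1 event to the new statin. Counting waking hours only (06:00 to 22:00) with dosing at 08:00 to 09:00 gives 2/16 to 3/16, or about 12% to 19%, still on assumptions. Nor are fasting and venepuncture confined to the pre-dose hours: the fast runs to 4 hours after dosing, and 18 of 19 draws (15 of 16 for simvastatin) come after it.

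Fourth, the case report form is not shown, and the list does not forbid a time field. That is true, and it leaves open that the form already does better than the protocol. It does not change what the protocol asks for.

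The point that survives is narrow: the specified fields cannot order Day 1 onsets against the dose.

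**Conclusion.** The point holds as a limited data-collection gap. From the fields that section 4.7.1.2 lists, Day 1 events before dosing cannot be told from those after it, so some may be misassigned in the by-statin safety summary. On the assumption of dosing at 07:00 to 10:00, the window is about 3% to 4% of study time, and 2.0% to 2.9% for confusion between two statins. How many events fall in it is unknown.

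The consequence is confined to a descriptive secondary summary with no safety hypothesis attached. The primary comparison of exposure is unaffected. The change is worth making because it is cheap before enrolment, while an onset time that was not recorded may be impossible to recover afterwards.

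**What to change.** In section 4.7.1.2, change the first two fields to start date and time and stop date and time. As a minimum, add a pre-dose/post-dose tick for events that begin on Day 1 of any period. Accept an estimated time, or the date alone, for events that arise during washout, where the volunteer is at home and date alone already places the event between two doses.

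The cost is one or two extra fields on the paper adverse event form. On Day 1 the volunteers are in-house, so the information is at hand. The rule that assigns each event to a statin can be left to the SAP.

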4.7.1.3 Reporting of serious adverse events

Investigators and other site personnel must inform appropriate AstraZeneca representatives of any SAE that occurs in the course of the study within 1 day (i.e., immediately but no later than the end of the next business day) of when he or she becomes aware of it.

The AstraZeneca representative will work with the investigator to compile all the necessary information and ensure that the appropriate AstraZeneca Drug Safety Department receives a report by day one for all fatal and life-threatening cases and by day five for all other SAEs.

Follow-up information from the investigator on SAEs must also be reported within the same time frames.

If a non-serious AE becomes serious, this and other relevant follow-up information must also be provided to AstraZeneca within 1 day as described above. For a non-serious AE that become serious but which is not fatal or life threatening a report should be received within 5 days.

All SAEs have to be reported, whether or not considered causally related to the investigational product or to the study procedure(s). All SAEs will be recorded in the case report form. The investigator and/or Sponsor are responsible for informing the Institutional Review Board (IRB) and/or the Regulatory Authority of the SAE as per local requirements.

5. STUDY MANAGEMENT

5.1 Monitoring

5.1.1 Study monitoring

The monitoring of this study will be performed in accordance with the principles of Good Clinical Practice (GCP) as laid out in the International Conference on Harmonization (ICH) document “Good Clinical Practice: Consolidated Guideline”.

The specific requirements of the genetic part of the study will be discussed with the investigator(s) and other personnel involved with the study.

5.1.2 Data verification

It is a prerequisite of this study that the study monitor has direct access to source data for data verification. This will be done by comparing data from the CRFs with those in the volunteer’s medical notes (permission from the volunteer will be sought as part of the consent process). Such verification is an essential element of quality control, as it allows the rectification of transcription errors and omissions.

Monitoring including source data verification should routinely be performed prior to the transfer of data to Data Management.

Source verification of the genetic consent of participating volunteers will be performed.

5.2 Audits and inspections

Authorized representatives of AstraZeneca, a regulatory authority, an IRB may visit the center to perform audits or inspections, including source data verification. The purpose of an AstraZeneca audit or inspection is to systematically and independently examine all study-related activities and documents to determine whether these activities were conducted, and data were recorded, analyzed, and accurately reported according to the protocol, GCP guidelines of the ICH and any applicable regulatory requirements. The investigator should contact AstraZeneca immediately if contacted by a regulatory agency about an inspection at his or her center.

5.3 Training of staff

The principal investigator will maintain a record of all individuals involved in the study (medical, nursing and other staff). He or she will ensure that appropriate training relevant to

the study is given to all of these staff, and that any new information of relevance to the performance of this study is forwarded to the staff involved.

Before the first volunteer is entered into the study the investigational staff will have an opportunity to discuss the procedures associated with the collection of blood samples, extraction of DNA and genetic testing with AstraZeneca personnel. The ethical considerations specific to genotyping and the importance of the informed consent process will be made clear. The requirements for the collections of the volunteers' samples will also be made clear.

5.4 Changes to the protocol

Study procedures will not be changed without the mutual agreement of the principal investigator and AstraZeneca.

If it is necessary for the study protocol to be amended, the amendment and/or a new version of the study protocol must be notified to or approved by the IRB. Local requirements must be followed.

If an administrative change is required, such a change must be notified to or approved by each IRB according to local requirements.

If a protocol amendment requires a change to the Informed Consent Form, then AstraZeneca and the IRB must be notified. Approval of the revised Master Informed Consent Form by AstraZeneca and by the IRB is required before the revised form is used.

AstraZeneca will distribute amendments and new versions of the protocol to the principal investigator who in turn is responsible for the distribution of these documents to his or her IRB, and to the staff at his or her center. The distribution of these documents to the regulatory authority will be handled according to local practice.

5.5 Study agreements

The principal investigator must comply with all the terms, conditions, and obligations of the study agreement for this study. In the event of any inconsistency between this protocol and the study agreement, this protocol shall prevail.

5.6 Study timetable and end of study

5.7 Data management

5.7.1 Case report forms

Paper CRFs (pCRFs) will be used to record data. Data should be recorded legibly onto the pCRFs in blue or black ballpoint pen. Correction fluid or covering labels must not be used.

The AstraZeneca monitor will check data at the monitoring visits to the study site. The investigator will ensure that the data in the pCRFs are accurate, complete and legible.

Data from the completed pCRFs will be entered onto AstraZeneca's clinical study database and validated under the direction of the Data Manager. Any missing, impossible or inconsistent recordings in the pCRFs will be referred back to the investigator using a data query form and be documented for each individual volunteer before clean file status is declared.

5.7.2 Genetic data

In the case of genotypic data, only the date the volunteer gave consent to participation in the genetic research and the date the blood sample was taken from the volunteer will be recorded in the pCRF and database.

The genotypic data generated from the study will be stored in the AstraZeneca LIMS database or other appropriate system. This database is a secure database, which is separate from the database used for the main study. Some or all of the datasets from the main study may be duplicated within the AstraZeneca LIMS database for exploratory genetic analysis.

However, some or all of the clinical study dataset may be duplicated within the AstraZeneca LIMS database or other appropriate system for exploratory analysis.

5.8 Reporting of genotypic results

Results from any genetic research performed will be reported separately from the clinical study report. AstraZeneca will not provide individual genotype results to volunteers, their family members, any insurance company, an employer, clinical study investigator, general physician or any other third party, unless required to do so by law. The volunteer's DNA will not be used for any purpose other than those described in the study protocol.

Individual volunteers will not be identified in any report or publication resulting from this work. The data and results of this study may be reviewed with collaborators and published, but neither the volunteer's name nor any other personal identifiers will appear in any publication or report.

6. PHARMACOKINETIC, PHARMACODYNAMIC, SAFETY, GENETIC AND STATISTICAL METHODOLOGY

6.1 Pharmacokinetic / pharmacodynamic evaluation

6.1.1 Calculation or derivation of pharmacokinetic variables

The _____, will carry out the pharmacokinetic analyses.

The pharmacokinetic variables of rosuvastatin, atorvastatin, simvastatin and the relevant metabolites of each defined below will be calculated by non-compartmental methods using WinNonlin Enterprise version 4.1, Pharsight Corp., Mountain View, CA. The actual sampling times will be used in the pharmacokinetic calculations. The following parameters will be derived:

C_{\max}	the observed maximum plasma concentration following a single dose
AUC	area under the plasma concentration time curve; calculated by $AUC_{(0-t)}$ and then extrapolated to infinity by the addition of $(C_{\text{last}} / \lambda_z)$
$AUC_{(0-t)}$	area under the plasma concentration time curve from time zero to the last quantifiable plasma concentration (C_{last}); calculated using the linear trapezoidal rule
$t_{1/2, \lambda_z}$	half-life associated with the terminal slope (λ_z) of a semi logarithmic plasma concentration-time curve; calculated as $\ln(2)/\lambda_z$
t_{\max}	the time to reach the observed maximum plasma concentration following a single dose
λ_z	terminal elimination rate constant, calculated by log-linear regression of the terminal portion of the concentration time profile where there are sufficient data (a minimum of 3 plasma concentration values in the terminal log-linear phase, spanning an interval of at least 2 half-lives)
CL/F	apparent oral clearance, calculated as Dose/AUC; (parent compounds only)

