- summarize and compare the plasma exposure of rosuvastatin, atorvastatin, and simvastatin after a single dose in healthy Chinese and Japanese volunteers to the plasma exposure of Caucasian volunteers following a single dose by measuring maximum concentration (C_{max}) and area under the concentration curve from zero to infinity (AUC).

The secondary objectives of this study are to:

- summarize the pharmacokinetics of rosuvastatin, atorvastatin, and simvastatin and the relevant metabolites of each by calculating area under the curve of plasma concentration against time from zero to time of last quantifiable concentration ($AUC_{(0-t)}$), terminal elimination half-life ($t_{1/2\lambda_z}$), time of maximum concentration (t_{max}), terminal elimination rate constant (λ_z) and, (for parent compound only), apparent oral clearance (CL/F).
- calculate parent to metabolite ratios of rosuvastatin metabolites (N-desmethyl rosuvastatin, and rosuvastatin lactone), atorvastatin metabolites (ortho-hydroxy atorvastatin and para-hydroxy atorvastatin) and simvastatin acid.
- obtain deoxyribonucleic acid (DNA) samples.
- assess safety and tolerability

Study design

This is a single center, randomized, open label, 3-way crossover study in healthy Chinese, Japanese, and Caucasian volunteers.

Investigational product, dosage and mode of administration

Rosuvastatin calcium will be administered as a 20 milligram (mg) oral tablet. Atorvastatin calcium will be administered as a 40 mg oral tablet. Simvastatin will be administered as a 40 mg oral tablet.

Duration of treatment

Volunteers meeting inclusion/exclusion criteria and satisfactorily completing screening evaluations during the screening period will participate in a 29-day study that will include 3 in-patient periods (Treatment Periods A, B, C) lasting 4 nights and 5 days with washout periods of at least 7 days between each in-patient period.

Variables

- Pharmacokinetic

C_{max} and AUC of rosuvastatin, atorvastatin, and simvastatin will be the primary endpoints for this study to summarize exposure in the selected populations. A detailed description of the summaries will be described in the Statistical Analyses Plan (SAP).

Along with C_{max} and AUC, $AUC_{(0-t)}$, $t_{1/2\lambda_z}$, t_{max} , λ_z and, (for parent compound only), CL/F of rosuvastatin, atorvastatin, and simvastatin and relevant metabolites will be determined to summarize the pharmacokinetics in the selected populations.

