1.1 Background

1.1.1 Clinical pharmacology of rosuvastatin

Rosuvastatin has been studied in North American, European, and Asian volunteers. In clinical pharmacology studies in volunteers, peak plasma concentrations of rosuvastatin are reached 3 to 5 hours following oral dosing. Both C_{max} and area under the concentration curve from zero to infinity (AUC) increase in approximate proportion to rosuvastatin dose. The absolute bioavailability of rosuvastatin in Caucasian and Japanese volunteers is approximately 20% and 29% respectively.

Administration of rosuvastatin with food decreased the rate of drug absorption by 20% as assessed by C_{max} but there was no effect on the extent of absorption as assessed by AUC. Plasma concentrations of rosuvastatin do not differ following evening or morning drug administration. Significant LDL-C reductions are seen when rosuvastatin is given with or without food, and regardless of the time of day of drug administration.

Mean volume of distribution at steady state of rosuvastatin is approximately 134 litres and 69 litres in Caucasian and Japanese volunteers respectively. Rosuvastatin is approximately 88% bound to plasma proteins, mostly albumin. This binding is reversible and independent of plasma concentrations.

Rosuvastatin is not extensively metabolised; approximately 10% of a radiolabeled dose is recovered as metabolite. The major metabolite is N-desmethyl rosuvastatin, which is formed principally by cytochrome P450 2C9. In vitro studies have demonstrated that N-desmethyl rosuvastatin has approximately one-sixth to one-half the HMG-CoA reductase inhibitory activity of rosuvastatin. Overall, greater than 90% of plasma HMG-CoA reductase inhibitory activity is accounted for by rosuvastatin.

Following oral administration, rosuvastatin and its metabolites are primarily excreted in the faeces (90%). The terminal elimination half-life ($t_{1/2\lambda z}$) of rosuvastatin is approximately 19 hours.

After an intravenous dose, approximately 28% of total body clearance was via the renal route, and 72% by the hepatic route.

In vitro and in vivo data indicate that rosuvastatin clearance is not dependent on metabolism by cytochromes P450 3A4 and 2C9 to a clinically significant extent. Rosuvastatin also does not interact to a clinically significant extent with the p-glycoprotein transporter.

Please refer to the investigator's brochure (IB) for additional information.

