4.2 Pharmacokinetic measurements

Serial blood sampling for rosuvastatin and atorvastatin will be done pre-dose (within 30 minutes), and 0.5, 1, 2, 3, 4, 5, 6, 8, 10, 12, 18, 24, 30, 36, 48, 54, 60, and 72 hours post-dose.

Serial blood sampling for simvastatin will be done pre-dose (within 30 minutes), and 0.5, 1, 2, 3, 4, 5, 6, 8, 10, 12, 18, 24, 30, 36, and 48 hours post-dose.

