6.1.3 Calculation or derivation of pharmacokinetics

C_{\max} and t_{\max} for each volunteer will be determined by inspection of the plasma concentration-time profile. The λ_z will be calculated by log-linear regression of the terminal portion of the concentration-time profiles where there are sufficient data (a minimum of 3 plasma concentration values in the terminal log-linear phase, spanning an interval of at least 2 half-lives.) Terminal elimination half-life ($t_{1/2, \lambda_z}$) will be calculated as $0.693/\lambda_z$. The $AUC_{(0-t)}$ will be calculated by the linear trapezoidal rule ($AUC = AUC_{(0-t)} + C_{\text{last}}/\lambda_z$). $AUC_{(0-t)}$ will be extrapolated to infinity using λ_z to obtain AUC where there are sufficient data. Following the single dose administration of rosuvastatin, atorvastatin and simvastatin, the CL/F will be calculated as Dose/AUC.

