6.4.2 Description of variables in relation to hypotheses

The primary question is whether the magnitude of the ethnic effect (Chinese or Japanese vs Caucasian) is equivalent when atorvastatin is compared to rosuvastatin or when simvastatin is compared to rosuvastatin. The test statistics are the ratios of the primary parameter ratios. For AUC, for example, the ratios are:

- $\frac{[AUC(\text{Chinese})/AUC(\text{Caucasian})]_{\text{Atorvastatin}}}{[AUC(\text{Chinese})/AUC(\text{Caucasian})]_{\text{Rosuvastatin}}}$
- $\frac{[AUC(\text{Japanese})/AUC(\text{Caucasian})]_{\text{Atorvastatin}}}{[AUC(\text{Japanese})/AUC(\text{Caucasian})]_{\text{Rosuvastatin}}}$
- $\frac{[AUC(\text{Chinese})/AUC(\text{Caucasian})]_{\text{Simvastatin}}}{[AUC(\text{Chinese})/AUC(\text{Caucasian})]_{\text{Rosuvastatin}}}$
- $\frac{[AUC(\text{Japanese})/AUC(\text{Caucasian})]_{\text{Simvastatin}}}{[AUC(\text{Japanese})/AUC(\text{Caucasian})]_{\text{Rosuvastatin}}}$

Ratios of C_{\max} ratios and $AUC_{(0-t)}$ ratios will also be examined.

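### The 2-half-life span rule for lambda-z also decides whether AUC to infinity exists, so rosuvastatin AUC may be lost selectively for volunteers with half-lives above about 21-30 h

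*Protocol*

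**What the plan says.** The synopsis (Variables) names Cmax and AUC of the three parent drugs as what "will be the primary endpoints for this study to summarize exposure in the selected populations". AUC means zero to infinity, and section 6.4.5 bases the sample size on it.

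Section 6.1.1 allows lambda-z only from "a minimum of 3 plasma concentration values in the terminal log-linear phase, spanning an interval of at least 2 half-lives". Section 6.1.3 repeats the condition and uses lambda-z "to obtain AUC where there are sufficient data". No lambda-z therefore means no AUC.

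Section 1.1.1 says the terminal half-life "of rosuvastatin is approximately 19 hours" and that "peak plasma concentrations of rosuvastatin are reached 3 to 5 hours following oral dosing". Section 4.2 ends the rosuvastatin and atorvastatin schedule with samples at "18, 24, 30, 36, 48, 54, 60, and 72 hours post-dose".

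On the hypotheses, section 6.4.2 says: "The test statistics are the ratios of the primary parameter ratios". Rosuvastatin is the denominator of all four AUC ratios listed there. Ratios of ratios for Cmax and AUC(0-t) are also to be examined. Section 6.4.3 defines an evaluable volunteer by eligibility, completion and absence of major deviations. An estimable AUC is not required.

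**The concern.** A span requirement is a sensible guard on the precision of a reported half-life. Used as the gate for AUC, it removes volunteers according to the length of their half-life. Half-life shares clearance with AUC, so the missing values are probably not missing at random with respect to exposure.

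The gate is tighter for rosuvastatin than for atorvastatin. The atorvastatin brochure (Appendix D) gives a half-life of about 14 h, so two half-lives are 28 h, against 38 h for rosuvastatin. The values most at risk are those shared by all four AUC comparisons. If half-life differs between ethnic groups, the loss differs too and can shift the rosuvastatin ethnic ratio, which is the reference for the whole trial. Because an estimable AUC is not part of being evaluable, 27 evaluable volunteers need not mean 27 with a rosuvastatin AUC.

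**Working it through.** **The plan's own figure.** Section 6.4.5 gives 27 per group for limits 0.7 to 1.43, true ratio 1 and 90% power, but states no SD, so 27 cannot be reproduced directly. I read the 90% CI as two one-sided 5% tests (an assumption) and compare within-subject log differences between two groups, with SE = SD × √(2/n). Solving for 90% power at n = 27 gives SD = 0.394 (t-based). I use this below; it does not show that 27 is wrong.

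**Cut-offs (document figures only).** Two half-lives at 19 h are 38 h. With a quantifiable 72 h sample the fit must start by 72 − 38 = 34 h, that is, at the 30 h sample or earlier. The largest half-life that passes is (72 − start)/2:

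| Terminal phase starts | Largest half-life that passes |
|---|---|
| 12 h | 30 h |
| 18 h | 27 h |
| 24 h | 24 h |
| 30 h | 21 h |

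**Share lost (assumed variability).** The document gives no half-life CV, quantification limit or start of the terminal phase. Assume lognormal half-life, median 19 h, σ = √ln(1 + CV²), and a quantifiable 72 h sample. The share lost is 1 − Φ(ln(cut-off/19)/σ). For CV 30%, σ = 0.294, and for a 24 h start ln(24/19)/0.294 = 0.80, so the loss is 21%.

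| Start | CV 20% | CV 30% | CV 40% |
|---|---|---|---|
| 12 h | 1% | 6% | 12% |
| 18 h | 4% | 12% | 18% |
| 24 h | 12% | 21% | 27% |
| 30 h | 31% | 37% | 40% |

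**What is thrown away.** If decline is mono-exponential, the share of AUC beyond 72 h is exp(−ln 2 × 72/half-life): 7% at 19 h, 12.5% at 24 h, 17% at 28 h and 19% at 30 h. The AUCs just above the cut-offs would be more than 80% observed.

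**Bias (24 h start, CV 30%).** Let ρ be the correlation of log AUC with log half-life, and s the SD of log AUC. Truncation lowers a group's mean log AUC by ρ·s·φ(a)/Φ(a), where a = ln(24/median)/σ. Assume ρ = 0.3-0.5 and s = 0.4-0.5, so ρ·s runs from 0.12 to 0.25. For a Caucasian median of 19 h, φ(a)/Φ(a) = 0.369.

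- Asian median 13.5 h: φ(a)/Φ(a) = 0.060, and a true ratio of 2.0 reads 2 × exp(0.309 × 0.12 to 0.25) = 2.08 to 2.16. The 13.5 h is only illustrative: section 1.1.1 gives volumes of 69 and 134 L and bioavailability of 29% and 20%. With about 2-fold exposure, clearance is 1.45/2 = 0.725 of the Caucasian value, so the half-life ratio is (69/134)/0.725 = 0.71.
- Asian median 15% longer (21.85 h): φ(a)/Φ(a) = 0.606, and 2.0 reads 1.94 to 1.88.

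The largest shift is about 0.08 on the log scale, against a margin of ln(1/0.7) = 0.357.

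**Power (complete pairs, SD 0.394).** With equal loss in both groups: n = 24, 85%; n = 22, 81%; n = 19, 73%; n = 16, 61%. If only one group loses 20% or 30%: 86% or 82%.

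**Under a 20% extrapolation limit.** Mono-exponentially the cut-off is 72 × ln 2/ln 5 = 31 h whatever the start. At CV 30% the loss is 5% instead of 21% for a 24 h start. The two bias cases become 2.02-2.05 and 1.97-1.94.

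**The case against.** A reader might infer that the rule discards the primary endpoint and damages every ratio of ratios. The documents do not support that. Cmax is also primary and needs no lambda-z; the Cmax and AUC(0-t) ratios are untouched, and AUC(0-t) already goes through the same mixed model (6.4.4). A volunteer at 19 h passes: samples from 24 to 72 h span 48 h against the 38 h needed. Only an upper tail is at risk.

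It is also fair that the loss rates rest on assumed inputs. With the peak at 3-5 h, nothing shown establishes a terminal phase that starts as late as 24-30 h. At a 12 h start and CV 30% the loss is only 6%. Section 3.2.1 expects the doses to characterise the profiles completely, so a scenario in which the 72 h sample is unquantifiable should not carry the point. The mono-exponential extrapolated share does not sit easily with a late terminal phase and is only a guide. Half-life depends on volume as well as clearance, so longer half-life need not mean higher exposure. The direction of bias is therefore open. The power figures use a back-solved SD and complete pairs, whereas the mixed model still uses a volunteer's other AUCs.

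An extrapolation limit also selects on half-life, and its 31 h cut-off is close to the present 30 h limit for a 12 h start. The gain is therefore real only if the terminal phase starts later than that.

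The SAP may add sensitivity analyses. That does not remove the point, because the gate itself is fixed in the protocol.

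**Conclusion.** The point holds in limited form. The protocol ties a primary endpoint, and the one that sets the sample size, to a span rule that leaves little room for rosuvastatin. AUC may be inestimable above a half-life of 21 to 30 h, depending on where the terminal phase starts. The cut-offs follow from the document's own sampling times. The frequency does not: 1-40% over the assumed CVs and starts, with a quantifiable 72 h sample.

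Bias in the rosuvastatin ethnic ratio is modest. A true 2.0 reads about 1.88 to 2.16 in a complete-case comparison under the stated assumptions, in either direction. Power for the AUC ratios of ratios falls to roughly 81% at 20% loss in both groups, less sharply under the mixed model. The trial is not invalidated, but an avoidable, selective loss in the common denominator is worth removing before data are seen.

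**What to change.** In the synopsis, 6.1.1 and 6.1.3, apply the 2-half-life span only to the reporting of lambda-z and half-life. For AUC, accept lambda-z from at least 3 terminal points, flag the span and the percentage extrapolated for each profile, and retain AUC when the extrapolated part is at most 20%. The 20% figure is a proposal; it does not come from the documents.

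Pre-specify the AUC(0-t) ratios of ratios, which are already modelled, as the supporting sensitivity analysis of extent whatever the missingness. Do not make AUC(0-t) a primary measure that is switched in when missing AUC passes some threshold; that would make the choice of primary endpoint depend on the data.

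The cost is wording in the protocol and matching text in the SAP, with no extra samples or volunteers. The downside is that some AUCs will rest on a less precisely estimated lambda-z.
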